3.1 Analysis Sets

3.1.1 Safety Analysis Set

The Safety Analysis Set includes all subjects who have received any portion of at least 1 dose of FPA150.

The Safety Analysis Set will be used in the summary of subject disposition, demographics and baseline characteristics, as well as safety data and study treatment administration.

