3.1.3 DLT-Evaluable Analysis Set

The DLT-Evaluable Analysis Set includes all enrolled subjects in Phase 1 monotherapy and in combination with pembrolizumab who received at least 2 doses of FPA150, and completed Cycles 1 of treatment, or who experienced a DLT in Cycle 1.

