3.2 Subject Grouping

Subjects will be grouped according to the actual treatment they received. Subjects with the same dose level from the dose escalation and exploratory in Phase 1a for monotherapy and safety lead-in in Phase 1a and Phase 1b for combination will be combined for summary.

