7 SAFETY ANALYSES

Unless otherwise specified, all analyses will be performed using the Safety Analysis Set.

No formal comparisons of safety endpoints are planned.

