7.1.6 Summary of Adverse Events and Deaths

The number and percentage of subjects who experienced at least 1 TEAE will be provided and summarized by SOC, PT, and treatment group. For other AEs described below, summaries will be provided by SOC, PT, maximum severity, and treatment group

- TEAE
- TE SAE
- Summary of TEAE of Grade 3-5
- TEAE related to FPA150
- TEAE leading to FPA150 treatment discontinuation
- TEAE leading to death
- TEAE of dose limiting toxicity

A brief, high-level summary of AEs described above will be provided by treatment group and by the number and percentage of subjects who experienced the above AEs.

Multiple events will be counted only once per subject in each summary. AEs will be summarized in alphabetic order of SOC and then by PT in descending order of total frequency within each SOC. For summaries by severity, the most severe severity will be used for those AEs that occurred more than once in a subject.

In addition to the above summary tables, TEAEs will be summarized by PT only in descending order of total frequency.

All AE and recorded deaths for the safety population will be listed.

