7.1.7 Dose-Limiting Toxicity

The summary and listing of DLTs will be performed on the DLT-Evaluable Analysis Set. A summary of DLT will be provided by SOC, PT, and severity. All DLTs will be listed.

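### SAP 7.1.6 puts a DLT row in the adverse-event tables on the pooled Safety Analysis Set by default, while SAP 7.1.7 uses the DLT-Evaluable set, so Phase 1a DLT incidence may be printed diluted and inconsistently

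*SAP*

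**What the plan says.** SAP Section 7 opens with a default: "Unless otherwise specified, all analyses will be performed using the Safety Analysis Set". SAP 3.1.1 defines that set broadly: "The Safety Analysis Set includes all subjects who have received any portion of at least 1 dose of FPA150".

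SAP 7.1.6 then lists "TEAE of dose limiting toxicity" as one of the categories to be tabulated by system organ class, preferred term, maximum severity and treatment group. It adds an overview: "A brief, high-level summary of AEs described above will be provided by treatment group and by the number and percentage of subjects" with each listed category. No other analysis set is given for the DLT row.

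SAP 7.1.7 says: "The summary and listing of DLTs will be performed on the DLT-Evaluable Analysis Set". That summary is by system organ class, preferred term and severity; no breakdown by treatment group or dose level is mentioned. SAP 3.1.3 defines the DLT-Evaluable set as "all enrolled subjects in Phase 1 monotherapy and in combination with pembrolizumab who received at least 2 doses of FPA150" and completed Cycle 1, or who had a DLT in Cycle 1.

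Treatment groups are formed under SAP 3.2: "Subjects with the same dose level from the dose escalation and exploratory in Phase 1a for monotherapy" are combined, and so are the combination safety lead-in and Phase 1b combination patients.

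**The concern.** DLT incidence is a primary endpoint in Phase 1a (SAP 1.2.1) and is not an endpoint in Phase 1b (SAP 1.2.2). Protocol 9.4.1 promises a DLT summary for Phase 1a. Protocol 4.1.2.2 defines DLTs for Dose Escalation and the Combination Safety Lead-in, and SAP 1.1.2 keeps Dose Exploration toxicities out of the formal DLT calculation.

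A programmer following 7.1.6 as written would still print a DLT percentage per pooled treatment group, with the group's Safety Analysis Set count as denominator. Patients whose events cannot count as DLTs would enlarge the denominator and add nothing to the numerator. The percentage could then only fall, and it could disagree with the 7.1.7 table for the same treatment. The 7.1.6 percentage is also the only DLT figure that the SAP expressly orders by treatment group.

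**Working it through.** **The plan's own totals.** The documents give no DLT rate or DLT denominator, so planned enrolment is the only stated figure to reproduce (SAP 1.3). Phase 1a: 26 escalation + 22 lead-in + 20 exploration = 68, as stated. Phase 1b: 7 cohorts × 30 = 210. Total: 68 + 210 = 278, as stated.

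**Who is in each denominator.**

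| Patients | Formally assessed for DLT? | Safety Analysis Set (7.1.6 by default) | DLT-Evaluable set, read literally (7.1.7) |
|---|---|---|---|
| Dose Escalation | Yes | Yes | Yes, if 3.1.3 is met |
| Dose Exploration | No (SAP 1.1.2) | Yes, pooled with escalation at the same dose | Not excluded |
| Combination Safety Lead-in | Yes | Yes | Yes, if 3.1.3 is met |
| Phase 1b combination | No (not an endpoint) | Yes, pooled with lead-in | Not excluded |

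**Combination, from planned maxima.** Inputs: up to 10 lead-in patients at the recommended dose (SAP 1.1.1) and up to 30 Phase 1b combination patients (SAP 1.1.3). Assume one DLT in the lead-in; this is an illustration, not an observed count. Rate = DLTs / denominator.

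- Full lead-in of 10: 1/10 = 10%. After pooling: 1/(10 + 30) = 1/40 = 2.5%. Dilution 40/10 = 4-fold.
- Lead-in of 6: 1/6 = 16.7%. After pooling: 1/(6 + 30) = 1/36 = 2.8%. Dilution 36/6 = 6-fold.

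**Monotherapy at 20 mg/kg.** Protocol 2.2.5.4 reports no DLT in the escalation cohorts at any dose up to 20 mg/kg. Protocol 2.2.5.3 counts 2 + 2 = 4 patients treated at 20 mg/kg, and SAP 1.1.1 gives that dose as the monotherapy recommended dose. Up to 10 exploration patients may be added there (SAP 1.1.2). The rate is 0/4 = 0% without pooling and 0/14 = 0% with it. The percentage does not move; the table would only suggest that 14 patients, not 4, had been formally assessed.

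**If 3.1.3 is read literally.** Exploration and Phase 1b combination patients with two doses and a completed Cycle 1 would enter the 7.1.7 denominator as well. In the combination example it could approach 40. The two tables might then nearly agree, but both would be diluted.

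**The case against.** The strongest reply is that the Section 7 default applies only where nothing else is specified, and 7.1.7 does specify a set for DLTs. On that reading the 7.1.6 row inherits the DLT-Evaluable set. This is a fair reading, and it means a double report of the endpoint is not certain. It does not settle the matter. The overview is a single table whose other rows are on the Safety Analysis Set, and nothing in 7.1.6 tells the programmer to change the denominator for one row.

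The reply also limits consequence, and this stands. Analyses are descriptive (Protocol 9.3), no formal testing is planned (SAP 3.4), every DLT is listed (SAP 7.1.7), and dose decisions are made by the Cohort Review Committee under Protocol Tables 5 and 6, not from these tables.

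A reader might infer several stronger things that the documents do not support:

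- **That an over-limit rate such as 2/6 could be hidden as 2/16 or 2/40.** Tables 5 and 6 stop enrolment at a dose with two or more DLTs in six. Exploration is conditional on the dose clearing the DLT criteria, and Phase 1b opens only at an identified MTD or recommended dose. A dose that fails at 2/6 would not gain those patients.
- **That the combination dilution is 40/6, or 6.7-fold.** The 40 already assumes ten lead-in patients. Like for like it is 4-fold or 6-fold.
- **That the Safety Analysis Set consists of patients never assessed for DLT.** It contains the assessed patients plus others.
- **That the two denominators must differ.** Under the literal wording of 3.1.3 they might not differ by much.

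**Conclusion.** The point holds as a minor one. SAP 7.1.6 and 7.1.7 both call for a DLT tabulation, and the SAP does not say which reports the primary endpoint or that the 7.1.6 row follows 7.1.7. By default the 7.1.6 row falls on the Safety Analysis Set, pooled with patients outside formal DLT assessment.

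For the combination, one lead-in DLT could be shown at about a quarter to a sixth of its proper rate. This rests on three assumptions: cohorts fill to their planned maxima, there is exactly one DLT, and the default set is applied. For monotherapy escalation the reported data give 0% on either denominator, so only the apparent number assessed is overstated. The wording of 3.1.3 is part of the same defect, since moving the 7.1.6 row onto that set as now written would not guarantee a clean denominator. What is at stake is how the study report presents a primary Phase 1a endpoint; the dose decisions are not affected.

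**What to change.** 1. In SAP 7.1.6, delete the DLT entry from the list and from the overview. If it is kept, print the DLT-Evaluable denominator in that row and leave Dose Exploration and Phase 1b blank.
2. In SAP 7.1.7, state that this is the analysis of the Phase 1a DLT endpoint. Present it by dose level, with the number assessed shown and without the SAP 3.2 pooling.
3. In SAP 3.1.3, restrict the DLT-Evaluable set to Phase 1a Dose Escalation and Combination Safety Lead-in. Protocol 9.2 carries the same unrestricted wording, so note the clarification in the study report.

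Cost: a few lines of SAP text and one or two table shells. No new data are needed.

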7.1.7 Dose-Limiting Toxicity

The summary and listing of DLTs will be performed on the DLT-Evaluable Analysis Set. A summary of DLT will be provided by SOC, PT, and severity. All DLTs will be listed.

7.2 Clinical Laboratory Evaluations

Summaries of laboratory data will be provided in the Safety Analysis Set and will include data collected up to the last dose of study drug plus 28 days for subjects who have discontinued study drug, or all available data at the time of the final analysis data-cut for subjects who are ongoing at the time of the final analysis.

Treatment-emergent laboratory abnormalities are defined as values that increase at least 1 toxicity grade from baseline at any postbaseline time point. If the relevant baseline laboratory value is missing, any abnormality of at least Grade 1 observed within the time frame specified above will be considered treatment emergent.

Summary of laboratory abnormalities with CTCAE v4.03 will be provided by lab test and treatment group. Subjects will be categorized according to the most severe postbaseline abnormality grade for a given laboratory test.

A by-subject listing of laboratory test results collected throughout the study will be provided.

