5.1 Inclusion Criteria

5.1.1 Phase 1a Inclusion Criteria (Monotherapy and Combination Therapy)

Patients enrolling into **Phase 1a** must meet *all* of the following inclusion criteria:

- 1) Histologically confirmed solid tumors except primary central nervous system (CNS) tumors.
- 2) Disease that is unresectable, locally advanced, or metastatic.
- 3) Able to understand and sign an IRB/IEC)approved ICF prior to any study-specific evaluation.
- 4) Patients should be refractory to or intolerant of existing therapy(ies) known to provide clinical benefit for their condition.
- 5) All patients must have at least one measurable lesion at baseline according to RECIST v1.1; tumor sites situated in a previously irradiated area, or in an area subjected to other loco-regional therapy, are not considered measurable unless there has been demonstrated progression in the lesion.
- 6) Adequate washout for prior anti-cancer therapy (ie, ≥ 5 half-lives or 4 weeks since the last dose, whichever is shorter).
- 7) Availability of archival tumor tissue for retrospective biomarker analysis, or patient must undergo a fresh tumor biopsy during screening if archival tissue is not available (a biopsy is required for patients in the Phase 1a Dose Exploration portion). Archival tissue for patients enrolled in Cohort 1b1 (Breast Cancer) must be within 24 months prior to pre-screening.
- 8) Age ≥ 18 years at the time the ICF is signed.
- 9) Eastern Cooperative Oncology Group (ECOG) performance status of 0 or 1.
- 10) Life expectancy of at least 3 months in the opinion of the Investigator.
- 11) Willing and able to comply with all study procedures.
- 12) Prior radiotherapy must be completed at least 2 weeks before the first dose of study drug.
- 13) Prior radiopharmaceuticals (eg, strontium, samarium) must be completed at least 8 weeks before the first dose of study drug.
- 14) Prior surgery that requires general anesthesia must be completed at least one week before first dose of study drug administration. Surgery requiring local/ epidural anesthesia must be completed at least 72 hours before first dose of study drug administration. Patients must have recovered from any surgery.

15) Screening laboratory values must meet the following criteria:

Hematologic:

- a. Neutrophils ≥ 1200 cells/ μ L
- b. Platelets $\geq 75 \times 10^3/\mu$ L
- c. Hemoglobin (Hb) ≥ 9.0 g/dL

Renal:

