9.4 Statistical Analyses

9.4.1 Safety Analyses

Safety analyses will be performed separately within both phases of the study and for all patients combined. Data from all patients that receive any portion of at least one dose of FPA150 as monotherapy or one dose of FPA150 in combination with pembrolizumab will be included in the safety analyses. AEs, clinical laboratory information, vital signs, ECOG performance status, weight, ECGs, and concomitant medications/procedures will be tabulated and summarized. In addition, the incidence of DLTs in Phase 1a will be summarized.

Subject incidence of AEs will be summarized overall and with separate summaries for serious AEs, AEs leading to discontinuation, AEs leading to death, and NCI CTCAE Grade 3 or higher AEs. The patients' worst grade for each preferred term will be used for the summary of AEs by CTCAE grade. Treatment-related AEs and SAEs will also be summarized similarly.

Weight and vital signs will be summarized descriptively (N, mean, SD, median, minimum, and maximum). ECOG performance status will be summarized categorically and descriptively.

Shift tables displaying patient counts and percentages classified by baseline grade and maximum grade on treatment will be provided for laboratory data by cohort and overall as appropriate.

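### SAP 7.2 omits the protocol's laboratory shift tables without recording the change, and does not tie its worst-grade table to its own treatment-emergent definition

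*SAP*

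**What the plan says.** Protocol 9.4.1 (Safety Analyses) makes a specific commitment: "Shift tables displaying patient counts and percentages classified by baseline grade and maximum grade on treatment will be provided for laboratory data". The sentence goes on to ask for this by cohort and, where appropriate, overall.

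SAP 7.2 (Clinical Laboratory Evaluations) has three parts that bear on this.

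- A definition: "Treatment-emergent laboratory abnormalities are defined as values that increase at least 1 toxicity grade from baseline at any postbaseline time point". It comes with a rule for missing baselines, under which any abnormality of Grade 1 or more counts as treatment-emergent.
- A table: "Summary of laboratory abnormalities with CTCAE v4.03 will be provided by lab test and treatment group", with the counting rule "Subjects will be categorized according to the most severe postbaseline abnormality grade for a given laboratory test".
- A listing: "A by-subject listing of laboratory test results collected throughout the study will be provided".

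No shift table appears anywhere in the SAP. Its one section on changes from the protocol, 6.3, concerns efficacy and deals only with duration of response and progression-free survival.

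The incidence of clinical laboratory abnormalities is part of the primary safety endpoint in Phase 1a (SAP Table 5) and Phase 1b (SAP Table 6).

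**The concern.** Patients may enter with abnormal laboratory values. Inclusion criterion 15 in protocol 5.1.1 ("Screening laboratory values must meet the following criteria") sets limits that reach into the abnormal range: AST and ALT up to 3 × ULN, or below 5 × ULN with liver metastases; bilirubin below 1.5 × ULN; hemoglobin from 9.0 g/dL; platelets from 75 × 10³/µL. Criterion 18 carries these limits into Phase 1b.

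A table of worst post-baseline grade with no baseline condition cannot separate an abnormality that the patient brought into the study from one that appeared or worsened on treatment. The protocol's shift table exists to make that separation. With the shift table gone and the treatment-emergent definition attached to no output, the reader of a primary safety summary may be unable to tell which kind of abnormality is being counted.

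**Working it through.** The plan states no figure on this point, so there is none to reproduce. The check has two parts.

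**1. The texts side by side**

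| Element | Protocol 9.4.1 | SAP 7.2 |
|---|---|---|
| Baseline grade shown in a table | Yes, as one margin of the shift table | No |
| Maximum on-treatment grade shown | Yes | Yes |
| Treatment-emergent rule defined | Not for laboratory data | Yes |
| Rule invoked in the table specification | Not applicable | No |
| Change from protocol recorded | – | No |

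Neighbouring SAP sections are more explicit. Section 7.1.6 labels its adverse event summaries as treatment-emergent, and 7.3 asks for baseline and change from baseline for weight and vital signs.

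The next table shows how five possible patients would be counted on one test.

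| Baseline grade → worst grade | Literal worst-grade table | Treatment-emergent table | Shift table |
|---|---|---|---|
| 2 → 1 | Grade 1 | not counted | cell (2,1) |
| 2 → 2 | Grade 2 | not counted | cell (2,2) |
| 2 → 3 | Grade 3 | Grade 3 | cell (2,3) |
| 0 → 3 | Grade 3 | Grade 3 | cell (0,3) |
| 0 → 0 | not counted | not counted | cell (0,0) |

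The two readings differ on the first two rows. On either reading, rows three and four look the same. Only the shift table distinguishes all five.

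**2. Size on the literal reading (illustration)**

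Inputs:
- n = 30, the maximum Phase 1b cohort size (protocol 4.1.4; SAP 1.1.3).
- b = share entering with a Grade 1 or higher abnormality on a given test that then persists. The documents do not give it; 10% to 50% is assumed.
- e = probability of worsening by at least one grade, taken as equal with and without a baseline abnormality. The documents do not give it; 5% to 20% is assumed.

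Formulas:
- Literal any-grade incidence = b + (1 − b)e
- Treatment-emergent incidence = e
- Excess = b(1 − e); excess patients = 30 × b(1 − e)

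| b | e | Literal | Treatment-emergent | Excess | Excess patients of 30 |
|---|---|---|---|---|---|
| 10% | 5% | 14.5% | 5% | 9.5 points | 2.85 |
| 10% | 20% | 28% | 20% | 8 points | 2.40 |
| 30% | 5% | 33.5% | 5% | 28.5 points | 8.55 |
| 30% | 20% | 44% | 20% | 24 points | 7.20 |
| 50% | 5% | 52.5% | 5% | 47.5 points | 14.25 |
| 50% | 20% | 60% | 20% | 40 points | 12.00 |

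As e approaches 0, the excess approaches its upper limit of 30b: 3 patients at b = 10% and 9 at b = 30%. If the treatment-emergent definition governs the table, the excess is 0 throughout.

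**Where in the grades it would fall.** For platelets the documents set a bound. Entry requires at least 75 × 10³/µL, which is 75 × 10⁹/L. The DLT definition (protocol 4.1.2.2.1) places Grade 3 thrombocytopenia at 50 down to 25 × 10⁹/L and Grade 4 below 25. An unchanged entry value therefore cannot fill the Grade 3 or 4 rows. For other tests the documents do not tabulate the grade limits, so concentration in the lower grades is an expectation.

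**The case against.** The strongest reply is that SAP 7.2 does refer to baseline. The treatment-emergent definition stands just above the table specification, with its own missing-baseline rule ("If the relevant baseline laboratory value is missing, any abnormality of at least Grade 1 observed within the time frame specified above" is to count). If the definition does not govern the only laboratory summary, it serves no output, so it is reasonable to think that it was meant to. This stands. A reader might infer that the SAP ignores baseline, or that pre-existing abnormalities will certainly be reported as on-treatment incidence. The documents do not support either claim: misreporting follows on one of two readings, and the text does not settle which applies.

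Other points reduce the weight. Protocol section 9 says that deviations from planned analyses will be described and justified in the final report, and SAP 6.3 is titled for efficacy only. Its silence therefore shows that the SAP does not record the change, and no intent to conceal should be read into it. Clinically significant laboratory findings are also reported as adverse events (protocol 8.12.2) and summarised as TEAEs by maximum severity. Exclusion criterion 9 bars chemistry abnormalities that the investigator judges clinically significant. By-subject listings allow a manual check. The endpoint is worded without the term treatment-emergent, so even a literal worst-grade table does not contradict it.

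Two further inferences should be resisted. One is that the table pools high and low abnormalities of tests such as potassium: SAP 7.2 does not address direction, which is different from saying that they are merged. The other is that dose groups will appear to differ because of drug: that would need baseline imbalance, of which the documents say nothing, and no formal safety comparisons are planned.

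None of this replaces the missing table. A listing is not a summary, and a one-way table on either reading cannot show the starting grade.

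**Conclusion.** The point holds as a gap between protocol and SAP with an ambiguity attached. Three things are established from the text: the promised shift tables are absent, the SAP does not record their removal, and the worst-grade table is not explicitly limited to the treatment-emergent abnormalities that the same section defines.

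The consequence is conditional. On the literal reading, any-grade incidence is inflated by b(1 − e), at most about 3 to 9 of 30 patients for an assumed 10% to 30% entering abnormal and remaining so. On the treatment-emergent reading the inflation is nil, but a move from Grade 0 to 3 and a move from Grade 2 to 3 cannot be told apart. Both prevalence and persistence are assumptions.

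No test, decision rule or sample size is affected, because the analyses are descriptive. The change is still worth making, because laboratory abnormality incidence is a primary safety endpoint and the repair is cheap.

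**What to change.** In SAP 7.2:

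1. Restore the shift table of baseline grade by maximum on-treatment grade, by cohort or dose group and overall, as protocol 9.4.1 specifies. If it is to be dropped, record and justify that as a change from the protocol.
2. State that laboratory abnormality incidence is summarised using the section's own treatment-emergent definition. Keep the plain worst-grade table as a supplement, labelled as unadjusted for baseline.
3. In the table shells, present high and low directions separately for two-sided tests. This is a clarification, since the SAP does not address direction.

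The cost is a few lines of SAP text and one standard table from data already collected, using the baseline rule already in SAP 3.7.3. Reported incidence may be lower than in the unadjusted table.
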